4.7.2 Discontinuation of ATG

The ATG/placebo will be discontinued if any one of the following is observed:

- A total WBC count $<2,000$ cells/mm³ that persists up to 24 hours after the time of the planned infusion.
- A neutrophil count <800 cells/mm³ that persists up to 24 hours after the time of the planned infusion.
- A platelet count $<50,000$ cells/mm³ that persists up to 24 hours after the time of the planned infusion.
- The participant experiences exacerbation of Cytokine Release Syndrome (CRS) twice consecutively despite the use of glucocorticoids.
- If the investigator believes that the study treatment is no longer in the best interest of the participant

Participants who prematurely discontinue study treatment will remain in the study and undergo all efficacy and safety assessments.

[figure not shown]

Figure 7. Rules for Reducing or Holding Second Dose of ATG

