1 INTRODUCTION

1.1 Study Overview

Title	ATG-GCSF in New Onset Type 1 Diabetes
IND Sponsor	National Institute of Diabetes and Digestive and Kidney Diseases (NIDDK)
Conducted By	Type 1 Diabetes Trial Network (TrialNet)
Protocol Chair	[name]
Accrual Objective	84
Study Design	Three-arm, 1:1:1 randomized, placebo controlled, double-blinded trial in which at least 28 subjects will receive active ATG-GCSF, at least 28 subjects will receive ATG alone and at least 28 subjects will receive placebo alone within 100 days from diagnosis of T1D. An adaptive design will be used to determine the variance of C-peptide over time and may require additional subjects to be enrolled in each group to preserve power.
Treatment Description	ATG will be administered at a dose of 2.5mg/kg as two divided IV infusions of 0.5mg/kg and 2mg/kg. GCSF will be administered at a dose of 6mg SC or if <44.5 kg a dose of 100 mcg/kg every two weeks for a total of 6 doses.
Study Duration	Enrollment is expected to occur over two-three years. Subjects will be followed up to 24 months from randomization in this protocol.
Objective	To determine the safety and ability of low dose ATG plus GCSF and low dose ATG alone to retain/enhance C-peptide production in new onset T1D patients demonstrating residual beta cell function.
Primary Outcome	The primary statistical hypothesis to be assessed in the study is whether the 2 hour area under the curve (change in baseline to 12 months) in residual beta cell function (C-peptide) will differ between those treated with ATG and GCSF or ATG alone as compared with placebo.
Secondary Goals	The study will also examine the effect of the proposed treatments on surrogate markers for immunologic and metabolic outcomes
Major Inclusion Criteria	Type 1 diabetes diagnosed within the past 100 days Age \geq 12 years < 46 At least one diabetes associated autoantibody

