4.5.2 ATG / Placebo Administration

All participants will be admitted to the hospital for the duration of the infusions and will be discharged no sooner than 12 hours after ATG infusion has been completed. Body weight at baseline (Time 0 – admission for the ATG/placebo infusion) will be used in calculating the doses for all infusions. Allowance in dose administration will be within +/- 5% of calculated dose.

To minimize the risk for thrombophlebitis associated with ATG infusion, 1000 units of heparin and 20 mg of hydrocortisone will be added to the ATG infusion bag for each dose given via peripheral intravenous administration. Since there is only a slight risk for thrombophlebitis for placebo infusion, the heparin and hydrocortisone will not be included in the infusion bag.

The first dose (0.5mg/kg) will be infused over a minimum of 12 hours, and the second dose (2mg/kg) over a minimum of 8 hours. The second dose should be given no less than 12 and no more than 24 hours after the previous dose. A maximum of 60 hours from the start of the first IV infusion will be allowed to complete all IV study drug (see parameters below). If a subject has not completed the two IV study drug infusions at the 60th hour, the infusion will be discontinued and they will not receive additional study drug. Vital signs will be checked every 30 minutes for the first 2 hours of the study drug infusion and thereafter at 60-minute intervals or as indicated for clinical signs or symptoms. Blood for laboratory testing should be drawn at least 8 hours after completion of each infusion in order to obtain reliable and comparable results.

Information about subject's clinical signs and symptoms related to ATG infusion will be captured on infusion CRFs. Those that are Grade 2 or more will be considered AEs and reported as such.

4.6 Premedication:

To reduce the risk of adverse reactions to ATG infusion, methylprednisolone 0.25 mg/kg IV will be given no less than 30 minutes before each infusion of active drug and 0.25 mg/kg IV will be given 12 hours (\pm 15 min) after the start of each infusion of active drug.

Placebo group: A placebo (saline) infusion similar in appearance will be given no less than 30 minutes before and 12 hours (\pm 15 min) after the start of each infusion.

Both groups: Participants in both groups will be pre-medicated with an antihistamine and acetaminophen PO at least 30 minutes before each infusion and every 4–6 hours as needed during the infusion, as follows:

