- Diphenhydramine 1.25 mg/kg/dose to a maximum of 50 mg.
- Acetaminophen 10–15 mg/kg/dose to a maximum of 650 mg.

4.6.1 Cytokine Release Syndrome:

With ATG infusion, the subject may experience Cytokine Release Syndrome (CRS). The signs and symptoms can span a wide clinical spectrum.

Mild Reactions: For mild (grade 1) reactions per the NCI-CTCAE for CRS, the study medication will be continued. The investigator shall take one or more of the following actions, depending on the type of the reaction:

1. Administer additional doses of antihistamine and acetaminophen.
2. Reduce the rate of infusion by 50% or more.
3. For chills and rigors, meperidine may be considered.

Moderate Reactions: For moderate (grade 2) reactions per the NCI-CTCAE for CRS, the study medication may be interrupted. The investigator shall take the following actions, depending on the type of the reaction:

1. Interrupt infusion if any of the following occurs:
 - a. Oral temperature of $> 40.0^{\circ}\text{C}$
 - b. Symptomatic bronchospasm or pulmonary edema
 - c. Allergy-related edema
 - d. Hypotension
2. When the temperature is $< 38.5^{\circ}\text{C}$ and signs and symptoms improve, restart ATG.
3. Closely monitor the subject with pulse oximetry and a blood pressure monitoring; provide ongoing nursing evaluation until at least 2 hours after the infusion is completed.
4. If necessary, glucocorticoids can be given every 6 hours at a dose of 0.5 mg/kg of methylprednisolone or equivalent.
5. If a subsequent dose of ATG further exacerbates the signs and symptoms of CRS despite following the above guidelines, the study treatment must be permanent discontinued.
6. Additional supportive or resuscitative measures (such as the use of epinephrine) may be needed if clinically indicated.

Severe Reactions: For severe (grade 3) reactions or greater per the NCI-CTCAE for CRS, the study medication will be permanently discontinued.

[figure not shown]

Figure 5. Rate Adjustments in Response to Cytokine Release Syndrome

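### Sections 4.6.1 and 4.7.2 of the protocol set different CRS triggers for stopping ATG, and the low-count window in 4.7.2 runs from an undefined time

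*Protocol*

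**What the plan says.** **CRS.** The protocol deals with stopping ATG for cytokine release syndrome in two places.

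- Section 4.6.1, item 5 for moderate (grade 2) reactions, makes this the ground for a permanent stop: "a subsequent dose of ATG further exacerbates the signs and symptoms of CRS despite following the above guidelines, the study treatment must be permanent discontinued". Item 4 of the same list makes steroids optional: "If necessary, glucocorticoids can be given every 6 hours". For grade 3 or higher, 4.6.1 adds: "For severe (grade 3) reactions or greater per the NCI-CTCAE for CRS, the study medication will be permanently discontinued".
- Section 4.7.2, the list headed as the discontinuation rules for ATG, gives this CRS item: "The participant experiences exacerbation of Cytokine Release Syndrome (CRS) twice consecutively despite the use of glucocorticoids".

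Section 1.1 describes the course as "two divided IV infusions of 0.5mg/kg and 2mg/kg".

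**Low counts.** Section 4.7.2 stops ATG for a white cell, neutrophil or platelet count below its limit "that persists up to 24 hours after the time of the planned infusion". Section 4.5.2 states: "The second dose should be given no less than 12 and no more than 24 hours after the previous dose". Section 4.7.1 and Appendix 1 footnote 2 allow the repeat blood count up to 24 hours after infusion 1 is complete. Sections 4.5.2 and 4.7.1 also require all ATG to be finished within 60 hours.

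**The concern.** Both CRS rules address a participant whose reaction worsens despite management, but they differ in two ways: the number of worsenings (one or two in a row) and whether glucocorticoids must have been used. No passage says which section prevails, or that 4.7.2 only adds to 4.6.1. The heading of 4.7.2 makes it the natural place for a site to look.

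The count rule raises a similar problem. Three passages count 24 hours from infusion 1, while 4.7.2 counts 24 hours from a different and undefined point.

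At stake are participant safety and even ATG exposure across sites in the two active arms. Sites that rely on different sections could handle the same reaction or the same count differently.

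**Working it through.** **1. CRS rules side by side**

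| | 4.6.1 item 5 | 4.7.2 CRS item |
|---|---|---|
| Worsenings needed | 1, on a subsequent dose | 2, consecutive |
| Glucocorticoids | optional | must have been used |
| Consequence | permanent stop | stop |

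Take a participant with grade 2 CRS on infusion 1 whose signs worsen once on infusion 2 despite management. Section 4.6.1 requires a permanent stop. The CRS item of 4.7.2 is not met.

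Subsequent doses available = 2 infusions − 1 = 1. Counted per dose, two worsenings on subsequent doses cannot occur. The 4.7.2 item can operate if repeated episodes within one infusion count (4.6.1 does provide for interruption and restart), or if the initial reaction is itself taken as the first exacerbation. The text says neither. Under either reading the steroid condition still differs from 4.6.1.

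**2. The plan's own time limit**

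Inputs: infusion 1 lasts 12 to 20 h and infusion 2 lasts 8 to 16 h (section 4.1); the interval is 12 to 24 h (section 4.5.2), taken from completion of infusion 1, as 4.1 does for the 12 h minimum.

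Total = infusion 1 + interval + infusion 2

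- Maximum: 20 + 24 + 16 = 60 h, exactly the stated cap.
- Minimum: 12 + 12 + 8 = 32 h.

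The cap therefore fits a wait of at most 24 h after infusion 1.

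**3. The 4.7.2 window if it refers to infusion 2**

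End of window after infusion 1 = planned interval + 24 h

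- Infusion 2 planned at 12 h: 12 + 24 = 36 h, which is 12 h beyond the 24 h limit.
- Infusion 2 planned at 24 h: 24 + 24 = 48 h, which is 24 h beyond it.

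Total time if infusion 2 started at the end of that window:

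| Infusion 1 / infusion 2 | Wait 36 h | Wait 48 h |
|---|---|---|
| 12 h / 8 h | 56 h | 68 h |
| 12 h / 16 h | 64 h | 76 h |
| 20 h / 8 h | 64 h | 76 h |
| 20 h / 16 h | 72 h | 84 h |

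One of the eight cases fits within 60 h, and it still exceeds the 24 h interval in 4.5.2.

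The cap alone does not remove the conflict. With the shortest infusions it leaves room for a wait of 60 − 12 − 8 = 40 h. A count that recovers 30 h after infusion 1 (12 + 30 + 8 = 50 h in total) is then not a stop under 4.7.2 and fits the cap, yet it lies outside 4.5.2, 4.7.1 and footnote 2.

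**4. The window if it refers to completion of infusion 1**

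All four passages give 24 h and there is no conflict. Only the wording of 4.7.2 needs correcting.

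**The case against.** The strongest reply is that 4.7.2 lists conditions each sufficient for stopping and does not claim to be exhaustive. No passage tells a site to continue when a 4.7.2 item is unmet, so a site that obeys both sections stops under 4.6.1. Section 4.7.2 also lets the investigator stop in the participant's interest. This stands, and it limits the CRS point: the text does not license continuing. What remains is that the CRS item in 4.7.2 then adds little, and that it misleads anyone who uses 4.7.2 as the stopping list.

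A reader might infer that 4.7.2 contradicts 4.6.1 because it omits grade 3 CRS. The documents do not support that. The grade 3 stop in 4.6.1 stands on its own, just as the stop for grade 4 allergic reactions sits in 4.6.2 and is likewise absent from 4.7.2.

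A reader might also take 36 hours as the protocol's rule, or infer that 4.7.2 authorises a late full dose. Neither follows. The 36 to 48 hours depend on reading the planned infusion as infusion 2, and 4.7.2 says only when to stop. That reading is nevertheless a natural one, since the count after infusion 1 governs the timing of infusion 2 (section 4.1) and the caption of Figure 7 concerns the second dose.

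Figures 4, 5 and 7 are not shown in the text at hand and may clarify the intention. The differing sentences would still need to be aligned.

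**Conclusion.** The CRS mismatch is firm on the text: one worsening with optional steroids in 4.6.1, against two consecutive worsenings despite steroids in 4.7.2, in a course with one subsequent dose and no stated precedence.

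The count mismatch is conditional. It amounts to 12 to 24 hours beyond the limits elsewhere if the planned infusion means infusion 2, and to nothing if it means completion of infusion 1. The undefined reference time is a defect under either reading.

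This is a clarification of safety rules, not a flaw in the statistical design. Participants who stop ATG stay in follow-up (4.7.2) and in their assigned group for analysis (5.6). No sample size, power or type I error figure depends on the point. The share of participants affected cannot be derived from the protocol.

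**What to change.** - Reconcile item 5 of 4.6.1 with the CRS item of 4.7.2 so that a single criterion applies, or state which section prevails. If the 4.7.2 item is kept, say whether episodes are counted per infusion or within an infusion, and whether prior glucocorticoid use is a condition.
- Define the reference time for the count window in 4.7.2, and make it agree with 4.5.2, 4.7.1, Appendix 1 footnote 2 and the 60-hour cap. Check Figures 4, 5 and 7 against the result.

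Which CRS criterion and which window are right is for the clinical team. The cost is a protocol clarification and a memo to sites, with no new procedures.

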4.7.3 Serum Sickness

Serum sickness from host immunization against rabbit protein may occur 7–15 days after the first dose of ATG. The patient may require glucocorticoid treatment for supportive care. The dose will depend on the severity of signs and symptoms. Each subject who develops signs or symptoms concerning for serum sickness will undergo a centralized review to ensure consistent decision making on the use of steroids. For subjects greater than 50kg, we recommend Prednisone as follows: Days 1-3, 50 mg every 12 hours, Day 4, 40 mg every 12 hours, Day 5, 30 mg every 12 hours, Day 6, 20 mg every 12 hours, Day 7, 10 mg every 12 hours. For subjects less than 50kg we will provide Prednisone as follows: Days 1-3, 30mg every 12 hours, Day 4, 20mg every 12 hours, Day 5, 10 mg every 12 hours, Day 6, 5 mg every 12 hours, Day 7, 5 mg once. Clinical judgment should be used in augmenting additional steroid therapy to provide the least amount of steroid required to provide symptomatic relief of serum sickness.

4.8 GCSF

GCSF is a covalent conjugate of recombinant methionyl human granulocyte colony stimulating factor (filgrastim) and monomethoxypolyethylene glycol. GCSF is a Colony Stimulating Factor that acts on hematopoietic cells by binding to specific cell surface receptors, thereby stimulating proliferation, differentiation, commitment, and end cell functional activation. GCSF is supplied in 0.6 mL prefilled syringes for subcutaneous injection. Each syringe contains 6 mg GCSF (based on protein weight), in a sterile, clear, colorless, preservative-free solution (pH 4.0) containing acetate (0.35 mg), sorbitol (30.0 mg), polysorbate 20 (0.02 mg), and sodium (0.02 mg) in water for injection, USP. The standard 6mg dose will be given with the exception of subjects who weigh less than 44.5 kg. For subjects who weigh less than 44.5kg, the dose of GCSF will be given as 100mcg/kg/dose. Dosing calculations will be made based on the weight at the previous visit unless there has been more than a 10% change. Allowance in dose administered up to +/- 5% of calculated dose is permitted.

4.8.1 GCSF / Placebo Administration

GCSF/Placebo treatment will begin 6 hours after completion of the ATG / Placebo. GCSF/Placebo will be given subcutaneously every 2 weeks for a total of 6 doses. Drug vehicle provided by the manufacturer will be used for the placebo injections.

4.9 Modification or Discontinuation of GCSF

Subjects will have a directed physical exam at each study visit and a CBC obtained every two weeks after the initiation of GCSF /placebo until they have completed study drug therapy. If at any time during the GCSF /placebo therapy the subject develops an ANC greater than $35 \times 10^9/L$, subsequent doses of GCSF /placebo will be given as placebo (regardless of study randomization) until the ANC is again lower than $35 \times 10^9/L$. A repeat CBC will be allowed once between scheduled doses to provide subjects an opportunity to normalize a previously elevated ANC. In addition, if splenomegaly is noted on physical exam, placebo will be given for the remainder of the drug course regardless of randomization.

4.10 Concomitant Medications

The use of concomitant medications will be assessed at each study visit and recorded on an appropriate source document and CRF. Participants are allowed to use preparations of insulin as advised by the investigator or the referring physician.

Participants will be requested not to use any of the following medications during the study.

- Agents that influence insulin sensitivity or secretion (pramlintide, sulfonylureas, metformin, diphenylhydantoin, thiazide, or other potassium-depleting diuretics, beta-adrenergic blockers, niacin).
- Vaccination with live vaccines from 6 weeks before enrollment to 3 months following last dose of study drug is not permitted. Killed vaccines other than influenza are discouraged during this time period.
- Any medication that may result in immunosuppression or immunomodulation.
- Systemic glucocorticoids (unless required during ATG administration or for the treatment of cytokine release syndrome or serum sickness).

If participants receive, or if the investigator believes that participants must receive, any of the above medications, the case must be discussed with the medical monitor and/or treating physician to determine if alternatives are available. The use of these medications must be documented on the source document and CRF.

4.11 Infectious Disease Screening

In general, no specific infectious diseases prophylaxis is warranted in this study. This decision is based on the limited duration and dose of exposure to ATG. In lieu of active serologic or virologic monitoring strategies, all subjects will be counseled on an ongoing basis on the importance of notifying their research centers about the presence of signs or symptoms suggestive of infection especially over the 1-2 months after the infusion. They will also be counseled on the importance of notifying the research center about potential exposures to varicella, influenza, or other infectious illnesses. In addition, during the first 2 weeks post ATG infusion, all research subjects will be contacted on a daily basis and queried about the presence of signs or symptoms (e.g. fever, rhinorrhea, cough, sore throat, mouth sores, myalgia, arthralgia, etc) that might represent markers of active infection. Specific algorithm(s) for the evaluation and management of those patients identified as having signs and/or symptoms concerning for infection are provided in the manual of operations for this study and are directed based on the participant's specific symptomatology. This will provide general and in some case specific recommendations for the assessment of patients.

All subjects will have EBV serology determined prior to study enrollment. Subjects who are EBV seronegative at screening must be EBV PCR negative within 30 days of randomization and may not have had signs or symptoms of an EBV compatible illness lasting longer than 7 days within 30 days of randomization. Additional EBV or other infectious disease monitoring will be done only if clinically indicated.

5 STUDY ASSESSMENTS

See Appendix 1 for detailed schedule of assessments

5.1 General Assessments

Study visits for all groups will occur according to the Schedule of Assessments .General assessments include:

- Medical history including lifestyle and participant experience assessment
- Physical exam
- Concomitant medications
- Adverse events

5.2 Laboratory Assessments

The following general laboratory assessments will be performed:

- Chemistry (sodium, potassium, chloride, CO₂, glucose, BUN, creatinine)
- Liver function tests (ALT, AST, alkaline phosphatase, total protein, albumin, total and direct bilirubin)
- Hematology (complete blood count with differential and platelets)
- CD4/CD8 ratio
- Serum IgG levels

At screening, these additional laboratory assessments will be performed:

- Interferon-Gamma Release Assay Test (IGRA)
- Diabetes Autoantibodies
- Antibodies to HIV, hepatitis B (antiHBcAb, HBsAg), hepatitis C (HCV), Cytomegalovirus (CMV IgG, IgM), and Epstein-Barr Virus (EBV IgG, IgM, EBNA₁CMV and EBV PCR)

Additional assessments include:

- Pregnancy test before each injection for all sexually mature women

5.3 Mechanistic Outcome Assessments

TrialNet will perform immune and genetic assays to further understand mechanisms that may be underlying the type 1 diabetes disease process and response to therapy. For this purpose, samples for PMBC, DNA, RNA, plasma, and serum may be obtained.

5.4 Metabolic Outcome Assessments

Metabolic assessments will consist of:

- Glucose records and reports of hypoglycemia

- Insulin dose
- HbA1c
- Mixed meal tolerance test (MMTT): 2 hour MMTT at 3, 6, 9 months, 4 hour MMTT at screening, 12, 18, and 24 months

5.5 Visit Windows

Randomization must occur within 100 days from diagnosis of T1D. The initial treatment should begin within 100 days from the day of diagnosis and generally within 37 days from the screening MMTT. With prior approval, this window may be extended to 56 days. All subsequent treatment visits and follow up visits in Appendix 1 must occur within the time limits specified below:

	Visit Windows
Visit -1:	At least 2 weeks before visit 0 and at least 21 days from diagnosis.
Visit 0:	Randomization < 100 days from diagnosis of T1DM and within 37 days from Visit -1.
Visits 1 through 6:	±3 days
Visits 7 through 9:	±7 days
Visits 10 and 11:	±14 days

5.6 Withdrawal from treatment

The study will be conducted according to the intent-to-treat principle. This means that once randomized into the study, a participant will be expected to undergo all scheduled follow-up assessments and will remain within the assigned treatment group for purposes of statistical analysis regardless of the actual course of treatment administered. Withdrawal from treatment does not automatically entail withdrawal from the study. Withdrawal from the study will only occur if the participant dies or withdraws consent. Subjects who withdraw consent are classified as inactive but may again become active upon re-entry into the study, if they so choose.

Withdrawal from treatment can occur for a number of reasons, some of which are outlined below.

A participant may elect to discontinue study medications, may be unable to continue them, or may be withdrawn (temporarily or permanently) at the discretion of the Principal Investigator if s/he determines that it is unsafe to continue or there is a significant change in the risk/benefit.

Non-pregnant individuals who are withdrawn from treatment should remain in the study and undergo scheduled assessment visits as appropriate and any additional visits as needed to address ongoing AEs. MMTT tests will not occur while an individual is pregnant.

